#### 6.6. Off study assessment

We will offer patients a follow-up evaluation at the NIH 6 months following being taken off EPAG treatment either due to lack of response or for the other reasons listed in §8.6, but this visit will

not be required. If they do not return to the NIH, we will contact their primary hematologist for information on their current hematologic status 6 months following their final dose of EPAG, and then take them off study.

If patients do return to the NIH at 6 months (± 30 days) for the off-study assessment, the following may be performed, and then the patient will be taken off study:

- Review of interval history and events, and physical examination
- Neurodevelopmental assessment (if previously performed)
- CBC with differential
- Hemoglobin F quantification by hemoglobin electrophoresis
- Erythrocyte adenosine deaminase
- Acute care panel (Na, K, Cl, CO2, Creatinine, Glucose, and Urea Nitrogen)
- Mineral panel (Phosphorus, Magnesium, Albumin, and Calcium)
- Hepatic panel (Alkaline Phosphatase, ALT, AST, Total Bilirubin, and Direct Bilirubin)
- Other (Total Protein, CK, Uric Acid, and LDH)
- Reticulocyte count
- Peripheral blood smear
- Bone marrow biopsy with reticulin and collagen staining and aspiration with cytogenetics
- Research blood as detailed in §7
- Iron panel (ferritin, transferrin, % saturation, total serum iron)
- MRI T2\* imaging to assess liver iron concentration, if being followed per above
- 24-hour urine collection to determine the total iron content at PI's discretion if indicated for iron
- Review of transfusion records (if available)

# 6.7. MRI Imaging to Assess Iron Loading

Liver iron concentration should be assessed using MRI-based techniques. Hepatic effective T2 (T2\*) magnetic resonance imaging sequences will be used, comparing observed signal relaxation to expected and experimentally derived controls to determine iron concentration. Native T1 mapping and fat-water separation sequences may also be obtained to better characterize the liver. Contrast is not required for these studies, and contrast allergy is therefore not considered exclusionary. The hepatic imaging will be targeted toward assessment of iron deposition of the liver and will not include a comprehensive abdominal assessment. Therefore, any additional questions of liver and abdominal pathology would require a separate clinical MRI scan. Although the sequences chosen should focus upon the liver, note will be made, where possible, of signal within the heart. Additional, cardiac-specific sequences are not required unless indicated for good clinical care. Likewise, imaging of other organs such as the brain, are not required, unless indicated clinically. Although it is expected that these imaging studies will be performed utilizing one of the

1.5 T scanners at the NIH Clinical Center for reasons of standardization, existing protocols, and scheduling constraints, the choice of device is not prescribed by this protocol and will be selected by the responsible imaging physicians(s). However, once selected, the same scanner will be preferentially used for all of the studies performed on a given patient to ensure comparability, or should the scanner be unavailable or be changed over the course of the study, at a minimum, a scanner with the same field strength will be used.

Imaging should be performed during the initial enrollment evaluation, and at the 6-month primary endpoint evaluation. For patients continuing treatment into the extended phase, it should be performed at the 6-month evaluation, and then annually (*i.e.* 12-month evaluation, 24-month evaluation, *etc.*) thereafter while on eltrombopag if the PI deems necessary. If eltrombopag is discontinued less than 3 months prior to a planned MRI evaluation, that evaluation should still be performed as was previously planned.

Inability to perform MRI imaging due to patient age, weight, or intolerance (e.g., claustrophobia), will not be reported to the IRB as a deviation, but will be noted within the medical record. If imaging is not obtained at a given timepoint, it should nonetheless be attempted at subsequent timepoints according to the above schedules and level of necessity.

# 6.8. Genetic analysis

Patients will undergo genetic testing as part of their initial enrollment assessments, if results are not available from a previous, outside assessment (see §6.1). Functional testing (e.g., ribosomal assembly, adenosine deaminase, *etc.*) will be considered for purposes of supporting a diagnosis of DBA but are not sufficient to substitute for genetic testing.

**Intended use:** The purpose of this analysis will be to identify, if possible, a disease-defining mutation and to rule-out alternative diagnoses; however, it is understood that approximately half of all patients so screened will not have an identifiable mutation (see §2.1). The presence of a disease-defining mutation is not required for study inclusion, nor is its absence considered exclusionary (see §4.1.1). This testing will also be important to rule-out the presence of MDS-defining mutations that would be considered exclusionary (§4.2.14). This testing will take one of two forms:

**Patients with a familial history of a known mutation:** For patients where a specific mutation known to cause DBA has been identified in a first-degree, biological relative (*i.e.* parent, sibling, or child), the appropriate gene-specific testing (e.g., direct sequencing, fluorescence-in-situ hybridization, *etc.*) will be performed by a CLIA-certified clinical laboratory.

**Patients without a familial history:** For patients without a familial history of DBA, or for which a specific, disease-causing mutation has not previously been identified, germline somatic mutation analysis will be performed using the NeoGenomics "Inherited bone marrow failure panel". If this specific test cannot be performed, a comparable CLIA-certified test encompassing known DBA genes is acceptable (e.g., University of Chicago "Hereditary Myeloid Malignancy and Inherited Bone Marrow Failure Panel", Cincinnati Children's Hospital "Bone Marrow Failure Syndromes Panel by next-generation sequencing", *etc.*). Unbiased whole-genome or whole-exome sequencing from outside, CLIA-certified sources provided by the patient or referring institution may be accepted at the PI's discretion.

**Privacy and Confidentiality:** The results of all genetic testing will be kept confidential. DBAspecific results (*i.e.* identification of a disease-causing mutation) will be linked to the anonymized, study-specific identifier assigned to patient at the time of enrollment to allow subgrouping of patient data the data analysis phase and for subgrouping of any banked biospecimens. This data will be stored on secure, NIH-maintained servers, accessible only to study personnel, and only for purposes of research. After review, the results of all genetic testing, including additional, clinically actionable variants will be scanned into the medical record (CRIS).

**Clinically Actionable Results:** Subjects will be contacted if a clinically actionable gene variant is discovered. Clinically actionable findings for the purpose of this study are defined as disorders appearing in the American College of Medical Genetics and Genomics recommendations for the return of incidental findings that is current at the time of primary analysis. Subjects will be contacted at this time and will be offered the opportunity to come to NIH (at our expense) to have genetic education and counseling to explain this result. If the subject does not want to come to NIH, a referral to a local genetic healthcare provider will be provided (at their expense).

This is the only time during the course of the study that incidental findings will be returned. No interrogations regarding clinically actionable findings will be made after the primary analysis.

# 7. Laboratory Research Studies

**Intended use:** Blood and bone marrow will be collected during the initial phase of this study at the baseline and 6-month landmark timepoints, and during the extended phase of this study every 6 months (for patients continuing on eltrombopag) or every 12 months (for patients for whom eltrombopag was discontinued during the extended phase). The volume to be collected shall be 60 mL of blood, or the lesser of either 3 mL/kg or 60 mL for pediatric subjects (less than 18 years of age), and 10 mL of aspirated bone marrow. These samples will be for use in the correlative laboratory research studies listed below.

Baseline samples may be obtained under 04-H-0012. Additionally, in selected patients we will collect urine for 24 hours at each of the landmark visits. These studies are not used in assessing the primary endpoint but are undertaken as descriptive or exploratory ancillary studies. Except for the urine studies all test will be performed on each subject's material.

- Extended peripheral blood and bone marrow flow cytometric phenotyping for cell surface or intracellular proteins (e.g. six color flow cytometry to measure primitive HSCs) and assessment of reactive oxygen species
- Hematopoietic progenitor colony, long term-culture-initiating cell, and in vitro erythrocyte differentiation assays for primitive cell content and function
- Studies to investigate pathways that can improve erythroid differentiation in DBA
- Studies to examine ribosome function and biology
- Evaluation of clonal dynamics (single/bulk cell whole exome/genome sequencing)
- mRNA expression studies (RNA seq) on blood or bone marrow cells
- Whole genome/exome/epigenome sequencing or targeted sequencing may be performed in this study to assess the presence of somatic mutations in genes known to be recurrently mutated in MDS/AML or novel recurrently mutated genes. The data obtained will be handled confidentially. The digital data will be password protected and available to only the relevant PI and co-investigators. The specimens will be used only to study the genetics of the rare disease. DNA will not be used for unrelated investigations unless permission is first granted by the NHLBI IRB as well as the subject. We do not intend to report mutations in genes associated with disease risk that are incidental to our research aims, commonly referred to as "incidental findings."
- Serum cytokine, chemokines and soluble receptor levels including but not limited to IFN- $\gamma$ , TNF- $\alpha$  and TPO levels.
- Pharmacokinetic studies of EPAG kinetics (selected patients)
- Should there be any remaining sample, it will be stored with the subject's permission for other exploratory laboratory research studies reviewed and approved by the IRB and listed in APPENDIX A: Schedule of Activities.

**Storage:** Research samples will be stored coded in the secure laboratory of [name].

**Tracking:** Samples will be ordered and tracked through the CRIS Research Screens. Should a CRIS screen not be available, the NIH form 2803-1 will be completed and will accompany the specimen and be filed in the medical record. Specimens will be entered in the NHLBI Biospecimen Inventory System (BSI). Samples will not be sent outside the NIH without an executed MTA.

**End of study procedures:** Samples from consenting subjects will be stored until they are no longer of scientific value or if a subject withdraws consent for their continued use, at which time they will be destroyed.

**Loss or destruction of samples:** Should we become aware that a major breech in our plan for tracking and storage of samples has occurred, the IRB will be notified.

# 8. Biostatistical Considerations

## 8.1. Objectives

The *primary objective* is to evaluate safety and efficacy of 6 months of therapy with eltrombopag in subjects with Diamond-Blackfan anemia.

The *secondary objectives* include assessments of the impact of eltrombopag upon rates of relapse and survival, clonal evolution, toxicities of extended therapy, the impact of treatment upon healthrelated quality of life and neurodevelopment in pediatric patients, and the impact of eltrombopag upon stem cell and erythroid cell dynamics and niche interactions including iron homeostasis.

#### 8.2. Endpoints

# 8.2.1. Primary endpoint

Primary efficacy endpoint will be the proportion of drug responders at 6 months. Best response (robust or not) will be noted, regardless of when it is achieved; however, for protocol purposes, primary response will be assessed according to patient status at the time of the 6-month primary endpoint assessment. Time-to-response will also be measured according to the time from eltrombopag initiation to the first time the patient met criteria for response.

*Response* to treatment will be defined by one or more of the following:

- Erythroid response for subjects with a pretreatment hemoglobin less than 9 G/dL will be defined as an increase in hemoglobin by >1.5 G/dL from enrollment baseline, *and/or*
- a reduction in the units of PRBC transfusions by at least 50% during the eight consecutive weeks prior to response assessment compared with the pretreatment transfusion number in the previous 8 weeks.

*Robust response* to treatment will be defined both:

- Stable hemoglobin (two consecutive measurements at least 2 weeks apart) greater than 10 g/dL, *and*
- Transfusion independence for the previous 8 weeks

For sub-analyses, *transient response* to treatment (robust or otherwise) is defined as any response meeting the respective criteria above within the first 6 months that is subsequently lost and not regained prior to the 6-month primary endpoint assessment. While note will be made of such patients, for the purposes of primary response analysis, these patients will be considered *non-responders* along with patients who fail to meet the above response criteria.

Primary safety endpoint will be the toxicity profile assessed at 6 months using CTCAE criteria.

*Transfusion Units:* In pediatric patients, the administration of red blood cell transfusions is typically weight based, typically 10-15 mL/kg, reaching a maximum of one bag of packed erythrocytes (300-350 mL). For protocol purposes, a "transfusion unit" for pediatric patients is 15 mL/kg of packed erythrocytes. For adults and pediatric patients weighing approximately 20 kg or greater, "units" will be measured in bags. Where ambiguity exists, the clinical record shall be reviewed to determine the intent of the ordering physician as to whether dosing was per-bag or on a weight basis. It will be the responsibility of the PI to adjudicate any remaining ambiguity. Transfusions administered for non-disease indications (e.g., trauma, acute blood loss, perioperative hemostasis, *etc.*) will be noted, but not included in statistical and response considerations.

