#### 4. Eligibility Assessment

#### 4.1. Inclusion criteria

In order to be participate in this study, individuals must meet all of the following criteria:

- 4.1.1. Diamond-Blackfan anemia defined as anemia presenting on or before the third year of life with reticulocytopenia and greatly reduced or absent bone marrow erythroid precursors, supported by, but not requiring either:
  - familial history
  - gene mutation testing demonstrating a known disease-causing mutation or a mutation of disease-associated gene in combination with clinical characteristics of DBA

Patients with late-onset DBA (diagnosed after the third year of life) may also be included if gene mutation testing confirms a disease-causing mutation as above.

- 4.1.2. Clinically-significant anemia as defined as either:
  - hemoglobin less than 9.0 g/dL
  - red cell transfusion of at least 2 units PRBC for adults or 30 cc/kg for children (whichever is less) in the eight weeks prior to study enrollment
- 4.1.3. Relapsed and/or steroid-refractory or intolerant of systemic corticosteroids
- 4.1.4. Age  $\geq$  2 years
- 4.1.5. Weight  $\geq$  12 kilograms
- 4.1.6. Residence within the United States of America or territories, or able to reside within the US or its territories while on drug during trial participation

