#### 8.2.2. Secondary endpoints

Secondary endpoints will include:

- Hematological responses at 3 months (as defined above)
- Time to response
- Best response, regardless of response status at primary endpoint
- Impact on platelet count and neutrophil count
- Relapse during the extension phase
- Clonal evolution, according to cytogenetic, mutational or flow cytometric markers
- Toxicities with extended duration of therapy
- The impact of treatment and treatment response on quality of life.
- Evaluation of neurodevelopmental changes at baseline and 6-month evaluations.
- Iron loading as measured by ferritin trends at each evaluation, and by iron staining of bone marrow biopsies at baseline and 6-month evaluations (and during extension at the PI's discretion)
- Evaluation of reactive oxygen species HSPCs (ROS flow cytometry assay at baseline and 6 months), and at interval evaluations during extended access at the PI's discretion

- Evaluation of global transcriptome in HSPCs (single cell RNA seq at baseline and 6 months)
- The impact of eltrombopag on reconstitution of the stem cell compartment (multicolor flow cytometry of bone marrow cells) and erythroid compartment (multicolor flow cytometry and CFU-E/BFU-E assays) at baseline and 6-month evaluations, and at interval evaluations during extended access at the PI's discretion

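### Time to response, best response and transient response rest on unconfirmed hits in a rolling 8-week transfusion window that is partly pre-drug before week 8

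*Combined protocol and SAP*

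**What the plan says.** Section 8.2.1 gives two routes to an ordinary response. One is a hemoglobin rise of more than 1.5 g/dL in subjects who start below 9 g/dL. The other is "a reduction in the units of PRBC transfusions by at least 50% during the eight consecutive weeks prior to response assessment". The comparator is one count of units taken over the 8 weeks before treatment. Besides month-6 status, three outcomes are built on this definition:

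- **Time to response:** "Time-to-response will also be measured according to the time from eltrombopag initiation to the first time the patient met criteria for response".
- **Best response:** "Best response (robust or not) will be noted, regardless of when it is achieved". Section 8.2.2 lists it, with time to response, as a secondary endpoint: "Best response, regardless of response status at primary endpoint".
- **Transient response (sub-analyses):** a response met at any point in the first 6 months that is lost and has not returned by the 6-month assessment.

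Robust response carries a repeat requirement: "Stable hemoglobin (two consecutive measurements at least 2 weeks apart) greater than 10 g/dL". Ordinary response carries none. Section 8.4 plans descriptive summaries, cumulative incidence and Cox regression for time to response, but adds no scoring rule. Section 6.3 schedules blood counts every 2 weeks. On study, transfusion records are reviewed only at the 3- and 6-month landmarks, when they can be obtained (section 6.4; Table 14).

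**The concern.** The transfusion criterion is a rolling count compared with a single 8-week baseline. With few transfusions in 8 weeks, a small shift in one date can halve the count. If the first or any such shift is scored as a response, the chance of a hit grows with every look. Before week 8 the window also contains time before the drug was started.

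The trial has one arm, so no control group would show how often this happens without treatment. At stake are the speed of response, the best-response rate and the number of transient responders.

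**Working it through.** **1. The plan's own figure.** Section 8.3 uses a two-stage minimax design: 15 subjects, stop if at most 1 responds; then 25 in total, accept the null if at most 5 respond. The chance of rejecting the null is the sum over x = 2 to 15 of P[Bin(15, p) = x] × P[Bin(10, p) ≥ 6 − x]. This gives 0.0328 at p = 0.10 and 0.802 at p = 0.30, in line with the stated 0.05 and 0.80. The design uses month-6 status only, and the week-24 window covers weeks 16-24, wholly on drug. The documents give no figure for chance response on the transfusion criterion.

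**2. Pre-drug content of the window.** At week t below 8 the window holds 8 − t weeks before first dose: 6 at week 2, 4 at week 4 and 2 at week 6.

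**3. One illustrative subject.** Take 2 units exactly every 29 days, on days −43, −14 and +15. The baseline (days −55 to 0) holds two episodes, or 4 units. The week-2 window (days −41 to 14) holds one episode, or 2 units. Since 2/4 = 50%, the criterion is met at week 2 with nothing changed.

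**4. Simulation with no drug effect.**

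- From the documents: the 8-week look-back and baseline; the 50% threshold; baseline entry by "red cell transfusion of at least 2 units PRBC for adults or 30 cc/kg for children" in the preceding 8 weeks (section 4.1), taken as at least 2 units; and a 2-week grid borrowed from the blood counts.
- Assumed, because the documents give no pattern: a constant transfusion rate; cycles of 2, 3 or 4 weeks with interval SD 0.5-1 week; 1 unit, 2 units or a mix of 1-2 per episode; or Poisson single units.
- A hit is units in (t − 8, t] ≤ 0.5 × baseline units.

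| Pattern | Any hit, weeks 2-24, fortnightly |
|---|---|
| 4-week cycles | 47-75% |
| Poisson, one unit every 3-4 weeks on average | 88-95% |
| 2- to 3-week cycles, fixed units | 2-31% |
| 2- to 3-week cycles, mixed 1-2 units | 18-49% |

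The 4-week result depends on irregularity. With 2 units per episode it is 0% at interval CV 0, 40% at 0.1, 62% at 0.2 and 67% at 0.3. For Poisson units at a mean of 4, 6 and 8 per 8 weeks it is 72%, 55% and 43%.

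**5. Scoring only at week 12 and month 6.** The 4-week case falls to about 12-28%. Transfusion responses can then be dated only to those two visits, while hemoglobin responses are dated fortnightly. Time to response would partly reflect which route was used.

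**6. Which feature drives the result.** Using only windows wholly on drug, the 4-week case is still 40-67%, against 47-75% with all windows. For Poisson units at a mean of 2/3/4/6/8 per 8 weeks, the share moves from 95/83/72/55/43% to 92/77/65/49/39%. Repeated unconfirmed looks drive most of it. Hits at weeks 2-6 still occur in about 16-30% of subjects on 4-week cycles with fixed units, and these are dated from partly pre-drug windows.

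**7. After the fix below.** Chance hits on 4-week cycles are about 6-18%, the upper end being mixed units. The single week-24 look gives 6-14% with fixed units. Strict persistence for a full further 8 weeks, with no allowance at month 6, would give about 0-0.2% with fixed units. For Poisson transfusion every 3-4 weeks the single week-24 look is itself 36-48%. The fix cannot go below that, because a month-6 hit still counts; strict persistence gives 24-37%.

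**The case against.** **The frequency is assumed.** Section 2.2 says about 20 transfusions are typically reached within the first year, which is 52/20 = 2.6 weeks between them or less. At 2.6 weeks the any-hit rate is about 10-27% with fixed units and 30-43% with mixed units. A reader might infer that half or more of all stably transfused subjects would score a response. The documents do not support that: it needs cycles of about 4 weeks or irregular transfusion, and fortnightly scoring. This objection stands.

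**The fortnightly grid is assumed.** Record review is scheduled only at week 12 and month 6. This also stands, but it does not remove the problem. Section 8.2.1 does not say which grid applies, and the sparse one creates the dating mismatch in step 5.

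**Pre-drug overlap is a minor cause.** Early windows share weeks with the baseline, and removing them lowers the rate only modestly. This stands. It leaves the dating fault in place.

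**The transient group need not be mostly artefact.** On 4-week cycles with fixed units, 40-61% of no-effect subjects would be labelled transient responders, so a reader might infer that most of that group is chance. That would require a true transient-response rate, which nobody has, and the group also includes hemoglobin and robust responses. The inference is not shown.

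**The stakes are limited.** The primary endpoint, the stage decisions and entry to the extension all use 6-month status, and transient responders count as non-responders. This stands and sets the scope.

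**Conclusion.** The point holds for two secondary endpoints, time to response and best response, and for the transient-response sub-analysis. As written, the first or any hit counts, with no earliest week, no scoring dates and no confirmation of an ordinary response. A response can therefore be dated to the drug from mostly pre-drug weeks, and chance hits accumulate over looks.

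The size depends on a transfusion pattern that the documents do not give. It runs from near zero on tightly regular 2- to 3-week cycles to about half to three-quarters on 4-week cycles with interval SD 0.5-1 week, and higher still if transfusion is fully irregular. All figures assume no drug effect, a constant transfusion rate and, unless stated, fortnightly scoring. Nothing here bears on the month-6 primary endpoint or the two-stage decision. It should be settled before analysis.

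**What to change.** In section 8.2.1, for time to response, best response and transient response, state that:

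- The transfusion criterion is scored from dated transfusion records on a named grid, using only 8-week windows that lie wholly after first dose (earliest week 8).
- Before month 6 it counts only if it holds at every assessment through the next non-overlapping 8 weeks, or up to and including the 6-month visit.
- Before month 6 the hemoglobin criterion must hold on two successive counts taken 2 or more weeks apart, as robust response already requires.
- A subject who meets criteria at the 6-month visit counts as a responder, dated to the start of the unbroken run ending there. These outcomes then agree with the primary endpoint.
- Residual chance hits are about the single-look rate (about 6-18% on 4-week cycles), not near zero. Near-zero figures belong to strict 8-week persistence with fixed units. That rule would leave a subject who first qualifies after week 16 as a primary responder with no confirmed date.

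**Cost.** This is analysis wording, plus making sure the records obtained at the landmark reviews carry transfusion dates; section 6.4 asks for records only when available. Response dates become later, and best-response and transient-response rates become lower. On a 2-week grid, a transient response by the transfusion route must begin by week 14 (14 + 8 = 22, before the week-24 visit).
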